**4) Number of Subjects\***

The study population will be comprised of 75 patients assigned to one of three groups of 25 COVID (+) patients each.

The proportion of subjects with AT3 levels < 100% will be 50/50 randomization of which 25 subjects with AT3 <100% will be standard of care and 25 subjects with AT3<100% will be standard of care with exogenous AT3 supplementation. The third group will be subjects with AT3 levels  $\geq 100\%$ .

- a. 25 patients with endogenous AT3 >100% who receive standard of care only or
- b. 25 patients with endogenous AT3 <100% who receive standard of care only or
- c. 25 patients with endogenous AT3 <100% who receive standard of care plus supplemental AT3.

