**7) Study Endpoints\***

The Primary endpoint is change from baseline in the ISTH DIC Score to Day 9.

The Secondary endpoints include change from baseline D-dimers, Fibrinogen & Prothrombin time, length of hospital stay (days), mortality (%), and Pulmonary function (including Time (days) to mechanical ventilation and/or ECMO Duration (days) of new ventilator or extracorporeal membrane oxygenation (ECMO) use, Change from baseline SOFA and SOFA Respiratory sub-score, Number of venous thromboembolisms, Number of major bleeding events

Subjects discharged prior to completion of intervention would be classified as having a successful outcome. We anticipate that all cause morbidity will occur in 10-20% of the COVID study population, despite standard of care. We anticipate that these patients will be deficient in endogenous AT3.

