### Dosing Rationale-

In those COVID(+) patients with an endogenous AT3 activity level <100% and at the discretion of the attending physician, Day 1 infusion of AT3 will be at a dose to be adjusted based on initial body weight up to 100 kg maximum and to a set target plasma activity level of 120% according to the following formula:

$$= \frac{(120\% - \text{baseline AT3}\%)}{1.4} \times \text{body weight (kg)}$$

Based on an example of an 85kg patient with a baseline AT activity level of 90%,

- The dose would be 1,821 units on a dosing schedule of Day 1, 3, 5, 7 & 9
- For a total of approximately 9100 units
- Each Thrombate III vial contains 500 units each reconstituted with 10 mL of Sterile Water for Injection, USP, the final concentration is approximately 50 units per mL.
- Requiring 4 vials per dose or 20 vials per patient

Each 85kg patient will receive ~9100 IU's over 5 doses requiring 20 vials

- (10% overage to account for any dose adjustments needed)
- therefore each patient would require 10,000 IU's
- for a total of 250,000 IU's or 500 vials for the study.

AT3 will be drawn every other day, pre-dose, for monitoring, and verification of 120% target plasma activity level. Dosing schedule will be as follows: Day 1, 3, 5, 7 & 9 a dose will be given if AT3 activity level remains less than 100% on those days, otherwise no dose will be given. Days refer to a 24 hour period.

Data to be collected from the medical record according to the Study Flowsheet (Appendix B) will include:

- a. Demographics: age, comorbidities, medical history, concomitant meds, vital signs, height and weight,
- b. ISTH DIC score and a Sofa Score,
- c. Laboratory values:
  - a. Platelets, PT, INR, PTT, D-Dimer, Fibrinogen, AT3 level, Anti-Xa,
- d. Outcomes:
  - a. Length of Stay, Mortality, change in PF ratio, Vent/ECMO days, # and severity VTE's, # and severity of bleeding events

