### **List of Expected Adverse Events**

Acute respiratory failure; respiratory distress; acute lung injury; acute respiratory distress syndrome (ARDS); acute renal failure; coagulation dysfunction; decreased platelets count; neutropenia; hypothermia; fever, bacteremia; sepsis, septic shock; hypotension; metabolic acidosis, pleural effusion; abdominal compartment syndrome; repeated surgeries/debridement; amputation.

For purposes of this study, deaths will be captured as clinical outcomes and do not need to be reported as SAEs unless felt related to study drug administration.

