## **24) Drugs or Devices**

### **Drug Administration, Dispensation and Disposition**

Once consent is obtained and necessary baseline data collected, and if the subject is enrolled and falls into the Thrombate III infusion arm, they will begin receiving THROMBATE III (Antithrombin III [Human]) at 120% target dose every other day for 9 days.

Study drug will be packaged, labeled, and delivered to the clinical center by the drug manufacturer. All medication supplied to be used in this study will be manufactured, tested, labeled, and released according to current legal requirements and Good Manufacturing Practice (GMP).

The pharmacy will conduct an inventory upon receipt of the clinical supplies and will acknowledge receipt of the supplies to the sponsor. A copy of the shipping documents will be maintained for records. Study drug will be stored in accordance with the package insert in a secure location until dispensed to the subject.

Study drug kits will be dispensed according to the dosing schedule. The pharmacy will keep a current record of the inventory and dispensing of all clinical supplies. This record will be made available to the sponsor's monitor for the purpose of accounting for all clinical supplies. Any discrepancy or deficiency will be recorded, with an explanation. All supplies sent to the investigator will be accounted for and in no case will clinical supplies be used in an unauthorized situation.

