**Appendix A**

**ISTH DIC**, the score is increased by 2 points for abnormal baseline D-dimers (fibrin-related marker) and/or abnormal fibrinogen <1.0 gram/L level (1 point). This scoring algorithm was developed by the ISTH Scientific and Standardization Committee (SSC) committee on DIC and published in 2001. The ISTH DIC is a set of objective criteria for the diagnosis and severity of DIC with a score of  $\geq 5$  correlating with overt DIC, whereas < 5 does not rule out DIC but may indicate DIC that is not overt. The score is only appropriate for use in patients with an underlying disorder that is known to be associated with DIC; e.g., sepsis, severe immunological reactions, etc.

The ISTH DIC score is calculated using

- platelet count ( $\geq 100,000 = 0$ ;  $50,000-99,999 = 1$ ;  $< 50,000 = 2$ ),
- fibrinogen level ( $\geq 100 \text{ mg/dL} = 0$ ;  $< 100 \text{ mg/dL} = 1$ ),
- prothrombin time prolongation above upper limit of normal (ULN)
  - ( $< 3 \text{ seconds} = 0$ ,  $3-6 \text{ seconds} = 1$ ,  $> 6 \text{ seconds} = 2$ ),
- and D-dimer ( $< 2 \text{ times ULN} = 0$ ,  $2-4 \text{ times ULN} = 2$ ,  $> 4 \text{ times ULN} = 3$ ).

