### Appendix C

The Secondary endpoint measurements:

- a. D-dimer level change from baseline to Day 9 in mcg/mL FEU or DDU,
- b. Fibrinogen level change from baseline to Day 9 in mg/dL
- c. Prothrombin time change from baseline to Day 9 in seconds
- d. Length of hospital stay in days,
- e. Mortality (%) of overall and between groups,
- f. Pulmonary function
  - a. Time (days) to mechanical ventilation and/or
  - b. ECMO Duration (days) or extracorporeal membrane oxygenation (ECMO) use,
- g. SOFA score change from baseline to Day 9 and
- h. SOFA Respiratory sub-score change from baseline to Day 9,
- i. Number of venous thromboembolisms from admission to hospital discharge,
- j. Number of major bleeding events from admission to hospital discharge

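### Early discharge is classed as a success, but that label has no value on the numeric Day 9 change in ISTH DIC score, and no other rule supplies one

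*Combined protocol and SAP*

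**What the plan says.** Section 7 (Study Endpoints): "The Primary endpoint is change from baseline in the ISTH DIC Score to Day 9". Later in the same section: "Subjects discharged prior to completion of intervention would be classified as having a successful outcome". It does not say which endpoint the label serves, or what counts as completing the intervention in a group that receives no infusion.

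Appendix A ("The ISTH DIC score is calculated using") awards 0–2 points for platelets, 0–1 for fibrinogen, 0–2 for prothrombin time and 0–3 for D-dimer. Section 8 has the score taken on Days 1, 3, 5, 7, 9 and 11. The discharge column of Appendix B contains no ISTH DIC score and none of its four laboratory components.

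Section 9 divides the study population into halves on change in SOFA and/or a score that it writes as ICH DC (read here as the ISTH DIC score), and compares the fastest with the slowest to recover. For missing continuous values it says only that imputation will be applied before statistics are computed. The one other missing-value rule, in Section 8, voids SOFA parameters that were not obtained clinically; it does not concern the DIC score.

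On death, the list of expected adverse events in Section 10 says: "For purposes of this study, deaths will be captured as clinical outcomes". On the length of treatment, Section 24 says "at 120% target dose every other day for 9 days", and the Dosing Rationale says that on Days 1, 3, 5, 7 and 9 "a dose will be given if AT3 activity level remains less than 100% on those days, otherwise no dose will be given".

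**The concern.** A change score needs a number for each patient, or a stated reason why a patient has none. Success is a category. No passage converts it into points, a rank or a responder definition, so a rule written for the primary endpoint cannot be applied to it. The plan also does not say whether the success label or the unnamed imputation governs a patient who goes home on, say, Day 5. The Day 9 laboratory changes in Appendix C, such as "D-dimer level change from baseline to Day 9 in mcg/mL FEU or DDU", have the same gap, and a patient who dies before Day 9 has no stated value or exemption.

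What is at stake is the direction of the result. If discharge differs between the randomised groups, leaving discharged patients out counts against the group that sends more patients home, while giving them the best score counts for it. Both choices are defensible, and the plan leaves the decision until the data can be seen.

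**Working it through.** **Scale.** The maximum is 2 + 1 + 2 + 3 = 8, so the score runs from 0 to 8 and the change from −8 to +8. The success label corresponds to no point on this scale.

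**Figures to reproduce.** None. The document gives no discharge rate, SD, effect size or sample-size derivation, so everything below is illustrative.

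**Assumptions.** True effect zero. 20% of group b (standard of care) and 40% of group c (AT3) are discharged before Day 9. The tendency to be discharged has correlation ρ = 0.3 to 0.7 with improvement. A plus sign favours AT3.

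**1. Discharged patients left out, normal scale.** If a share p leaves, the mean improvement of those who stay is −ρ·φ(z)/(1−p), where z is the upper p point of the standard normal.
- p = 0.20: z = 0.842, φ = 0.280, and 0.280/0.80 = 0.350.
- p = 0.40: z = 0.253, φ = 0.386, and 0.386/0.60 = 0.644.
- Difference, c minus b: −ρ × (0.644 − 0.350) = −0.294ρ. This is −0.09, −0.15 and −0.21 SD at ρ = 0.3, 0.5 and 0.7.
- With equal p the two terms cancel and the bias is zero.
- At a milder 20% v 30%, simulation gives −0.04 to −0.10 SD.

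**2. The integer score.** Simulated from Appendix A's cut-offs, with an assumed median D-dimer of 2.5 or 4 times the upper limit of normal, an assumed baseline mean of 1.7–2.3 points, and a resulting SD of change of 1.27–1.31 points; 20% v 40% discharged.
- Left out: −0.06 to −0.15 points. 0.06/1.31 = 0.05 and 0.15/1.27 = 0.12, so about 0.05–0.12 SD against AT3.
- Scored 0, the best score: +0.25 to +0.38 points. 0.25/1.31 = 0.19 and 0.38/1.27 = 0.30, so about 0.19–0.30 SD in favour of AT3.
- Equal 20% discharge: within 0.004 points of zero.

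Taking steps 1 and 2 together, leaving patients out costs AT3 about 0.05–0.21 SD, and scoring them 0 gains it about 0.19–0.30 SD. The sign follows the rule chosen.

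**3. Section 9 as written.** All 75 patients are split into halves, discharged patients are placed in the fastest half, and group a is discharged at 20% or 40%. In simulation, AT3 patients make up about 54–57% of the randomised patients in that half, against 50% with equal discharge.

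**4. A caution on single imputation.** Filling gaps with the arm mean and then testing as if the values had been observed gives a type I error of about 12% with 20% missing and 25% with 40% missing (25 per arm, nominal 5%), even when discharge is equal. This is a general fault of single imputation and not a consequence of the discharge rule.

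**The case against.** The best defence has four parts. This is a pilot. Mortality, thromboembolism, bleeding and length of stay each have their own secondary endpoint, so early discharge and death are not lost from view. The half-split in Section 9 could take discharged patients as fast recoverers, and the shift is then small. And Day 9 is the natural reading of when the intervention ends, from Section 24 and the fixed checks in the Dosing Rationale.

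Most of this limits the size and scope of the point, and that part stands. It does not close the gap. Section 9 never places discharged patients in the fast half, it tests at the 5% level, and Section 7 itself foresees early discharge. The Day 9 reading is sensible but should be written down.

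Several stronger readings are tempting and are not supported:
- *That the rule biases the trial towards AT3.* The document gives no discharge rates. The trial is open label and the attending physician may be an investigator (Section 5), so unequal discharge is possible, but it is not shown, and the bias could run either way.
- *That success could be scored as a very large improvement, such as 2 SD.* On the simulated score that is 2 × 1.27 to 2 × 1.31, or 2.5–2.6 points. A patient at the assumed mean baseline of 1.7–2.3 cannot improve that much on a score with a floor of 0.
- *That arm-mean filling is planned.* The plan does not propose it; it only names nothing else.
- *That outcome data stop at withdrawal.* Section 11 is silent, but Sections 6 and 8 and Appendix B point to continued capture.

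**Conclusion.** The point holds and should be fixed. The plan states a rule for early discharge that cannot be applied to its numeric primary endpoint, and neither the unnamed imputation nor the half-split fills the gap. Deaths before Day 9 and the Day 9 laboratory changes are left open in the same way.

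Confidence is high for the gap in the text and low for its size. The discharge rates, correlations and baseline scores are all assumed, and the effect vanishes if discharge is equal and one consistent rule is used. On the analysis that Section 9 describes, the effect is small. The larger figures, with opposite signs, belong to a comparison of groups c and b that a reader would expect from the randomisation but that Section 9 does not set out.

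**What to change.** 1. **Section 7.** Define early discharge as discharge alive before the Day 9 score, in the same words for groups a, b and c. Remove the success label from the numeric primary endpoint.
2. **Section 9.** Replace the unnamed imputation with an analysis of all observed Day 1–9 scores that compares groups c and b as randomised, by a repeated-measures model or by multiple imputation that carries its uncertainty. Do not impute scores after death; report deaths by group beside the primary result.
3. **Sensitivity analysis.** Keep the idea that discharge is a success as a prespecified ranking: death before Day 9 worst, then in-hospital change, then discharged alive. State where inpatients without a Day 9 score rank, for example by their last observed score.

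The cost is reworded text in two sections and a little more analysis. No visits are added, because the scores are already scheduled, and study treatment is unaffected.

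The model has limits. In simulation with about 19% v 37% discharged, it removed the bias when discharge followed earlier scores (0.06 SD with completers only, 0.00 with the model). When discharge followed the unseen current score, 0.059 of 0.105 SD remained. Patients who leave before Day 3 contribute only a baseline, and estimates with 25 per arm will be imprecise. The ranked analysis partly measures open-label discharge practice, which is why it should stay a sensitivity analysis.

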**14) Potential Benefits to Subjects\***

We expect subjects with deficient endogenous AT3 can lessen the risk associated with a prothrombotic hyperinflammatory state with infusion of AT3.

**15) Setting:** Jackson South Medical Center , Jackson Memorial Hospital

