**Appendix B**

Study Subject Flowsheet	Enrollment - Day 1*	Days 3, 5, 7 & 9	Day 11	On Discharge
Informed Consent	x			
Entry Criteria	x			
Demographics	x			
Medical and Surgical History	x			
Prior & Concomitant Medications	x	x	x	x
Vital Sign Measurements	x	x	x	
ISTH DIC Score	x	x	x	
SOFA Score	x		x	
Blood Draw	x	x	x	
Urine or Serum Pregnancy Test if applicable	x			
Platelet	x	x	x	
PT, INR	x	x	x	
PTT	x	x	x	
Hemoglobin and Hematocrit	x	x	x	
Fibrinogen	x	x	x	
D-Dimer	x	x	x	
AT3 Level	x	x	x	
Anti-Xa	x	x	x	
Dosing if randomized to group with AT3 Infusion 	x 	x 		
Adverse Events 	x	x	x	x 
Hospital LOS				x
Mortality				x
PF ratio change				x
Days on Ventilator				x
Days on ECMO				x
VTE's				x
Bleeding Events				x

\*: Day refers to a 24 hour period.

x: To be completed

1: Only if randomized to AT3 Infusion and AT3 level is at specified level

2: Only Serious Adverse Events will be captured from last dose to hospital discharge.

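### The early-discharge success rule depends on an undefined end of intervention that two of the three groups do not have, and it credits every kind of discharge

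*Combined protocol and SAP*

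**What the plan says.** Section 7 defines the primary outcome as a score change: "The Primary endpoint is change from baseline in the ISTH DIC Score to Day 9". It then adds a rule for subjects who leave early: "Subjects discharged prior to completion of intervention would be classified as having a successful outcome". The rule names no group, calendar day or discharge destination.

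Section 4 assigns 25 subjects to each of three groups. Groups a (AT3 above 100%) and b (AT3 below 100%) receive standard care alone. Group c (AT3 below 100%) receives standard care plus AT3. Groups b and c are the randomised pair.

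The documents describe dosing in group c in two ways. Under Dosing Rationale in section 8, doses are scheduled for Days 1, 3, 5, 7 and 9, but "a dose will be given if AT3 activity level remains less than 100% on those days, otherwise no dose will be given". Footnote 1 of Appendix B agrees: "Only if randomized to AT3 Infusion and AT3 level is at specified level". Section 24 says that subjects in the infusion arm receive the drug "at 120% target dose every other day for 9 days", with no such condition.

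Section 9 compares the faster-recovering half of the population with the slower half and does not mention a success category. Its only other relevant provision is a general statement that missing continuous values will be imputed, with no method given.

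**The concern.** The rule in section 7 is the only one that addresses early discharge specifically, and early discharge is a main way for a subject to lack a Day 9 score. It has two defects.

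- **The cut-off.** It depends on completing an intervention that only group c receives. Even in group c the end point is unclear, because dosing is conditional in one section and unconditional in another. Two subjects in different randomised arms with the same clinical course could therefore be labelled differently.
- **The event.** Any discharge qualifies. A subject moved to another acute hospital because of deterioration, discharged to hospice, or leaving against advice would be labelled a success. The discharge column of Appendix B has no field for destination, so the listed data could not separate these cases later.

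Both matter more here because the trial is open label (section 1) and the attending physician may be an investigator (section 5). An undefined cut-off also leaves the reading to be chosen after the data are known.

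**Working it through.** The documents give no figure to reproduce: there is no discharge rate, success rate or power calculation. The check is a comparison of readings, followed by an illustration.

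**1. Apply the rule to a subject discharged on Day 6.** Three readings of completion are possible:

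- A: the last dose that would be due under the conditional schedule (group c only).
- B: the end of the nine-day schedule (group c only).
- C: Day 9 for every group.

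| Subject discharged on Day 6 | A | B | C |
|---|---|---|---|
| Group c, a further dose would have been due on Day 7 or 9 | success | success | success |
| Group c, last dose on Day 1, 3 or 5 | not credited | success | success |
| Groups a and b | rule cannot apply | rule cannot apply | success |

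Only C treats the arms alike, and no section states it. Reading A also cannot be applied reliably. Whether a Day 7 dose was due depends on a Day 7 pre-dose AT3 level, which may never be drawn in a subject discharged on Day 6.

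**2. Illustration of what the choice of reading could do.** Let p be the true probability of discharge before Day 9, equal in groups b and c (n = 25 each), so there is no treatment effect. All p values are assumptions. The test is a two-sided Fisher exact test at 0.05; section 9 gives p < 0.05 but not the sidedness.

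*Credit in group c only, every early discharge credited (reading B).* Expected successes are 25p against 0: 25 × 0.20 = 5 and 25 × 0.40 = 10. A split of 5 against 0 gives P = 0.0502 and 6 against 0 gives P = 0.022. The chance of a spurious significant difference is therefore P(X ≥ 6) with X ~ Binomial(25, p):

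| p | Expected successes, c vs b | Chance of spurious p < 0.05 |
|---|---|---|
| 0.1 | 2.5 vs 0 | 3.3% |
| 0.2 | 5 vs 0 | 38.3% |
| 0.3 | 7.5 vs 0 | 80.7% |
| 0.4 | 10 vs 0 | 97.1% |

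*Opposite direction.* Credit group b up to Day 9 and group c only up to its last dose, with an assumed share q of early-discharged group c subjects already past that dose. The credited rate in c is p(1 − q).

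- p = 0.3, q = 0.5: 0.3 × 0.5 = 15% in c against 30% in b; spurious difference in 15.0% of trials.
- p = 0.5, q = 0.5: 0.5 × 0.5 = 25% in c against 50% in b; spurious difference in 35.8% of trials.

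*One calendar rule for both arms (reading C).* For p from 0.1 to 0.6 the chance of a spurious difference is 0.9% to 3.3%, within the nominal 5%.

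**3. Does the label reach a planned analysis?** The primary endpoint is a change in a score that runs from 0 to 8 (Appendix A: 2 + 1 + 2 + 3). No section says what Day 9 value a successful early discharge receives, and section 9 does not tabulate successes by group. The illustration therefore describes the label and not a planned result.

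**The case against.** The strongest reply is that Day 9 is the obvious cut-off for everyone. It is the primary endpoint day and the last scheduled dosing day, and the sentence speaks of subjects without limiting itself to one arm. On that reading the arms are treated alike. This is plausible and may be what was meant. It is still not written anywhere, and the words used point to something two groups do not receive. If Day 9 was intended, the repair only records it.

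The second reply is that the label enters no analysis, so it biases nothing. The premise is correct. It limits what can be said about harm, but it leaves a stated endpoint rule with no defined use.

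The third reply is that hospice and against-advice cases will be few. Section 3 excludes subjects with a do-not-resuscitate order, expected early death or palliative care, and section 11 allows withdrawal if such an order is made later or if the subject is unwilling to continue. This narrows those cases. Withdrawal is only a possibility there, and transfer to another hospital is not covered.

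A reader might also infer that, within group c, the rule rewards subjects whose AT3 failed to recover. That requires treating one restored level as the end of treatment. AT3 is retested every other day and dosing could resume up to Day 9, so the documents do not support the inference.

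**Conclusion.** The point holds as a defect in a stated rule. Completion of the intervention is undefined, does not exist for 50 of 75 subjects, and in group c rests on two dosing descriptions that must be reconciled. On its literal wording the rule is not neutral between arms. Separately, and on any reading of the cut-off, it counts unfavourable discharges as successes.

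A reader might go further and conclude that the trial is biased towards AT3 by 20 to 40 percentage points. The documents do not support that. The figure is simply the assumed early-discharge rate under one reading; another reading favours the control arm, and a common Day 9 cut-off gives no difference. With no discharge or AT3-recovery rates stated and no analysis that uses the label, neither direction nor size can be derived. Nor do the documents show how often transfers or hospice discharges would occur. The change is worth making because the rule as written can misclassify subjects in an open-label trial and is cheap to repair.

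**What to change.** Replace the sentence in section 7 with one calendar rule for all three groups, for example: subjects discharged alive before the Day 9 visit, other than to hospice, to another acute-care hospital or against medical advice, are classed as early discharge with successful outcome, regardless of group or doses received; the excluded discharges are not classed as successes.

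Three further changes are needed:

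- Add discharge destination to the discharge column of Appendix B.
- State in section 9 how the label enters the Day 9 comparison of groups b and c, including what is done with the score of a subject discharged early, whether or not classed as a success.
- Reconcile the dosing descriptions in sections 8 and 24. The calendar rule does not depend on which description stands.

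The cost is a few sentences and one chart field, with slightly fewer subjects classed as successes. No dose or clinical procedure changes.
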